2.2.3 Pre-Clinical Experience with MVA-Vectored Vaccines Expressing HIV Immunogens

Toxicity: A formal animal toxicity study of **M3** and **M4** has not been performed. We consider the more informative safety profile is the extensive clinical experience with similar MVA vectors. These studies, in part summarized in [Table 1](#) and [Table 3](#), have consistently shown MVA vaccination is safe and well tolerated at the dose and IM route proposed in this trial, and in both HIV positive and seronegative men and women.

A pre-clinical GLP toxicology study of MVA.HIVconsV (UNO 0011) assessed the systemic toxic potential of 2×10^7 pfu/dose of MVA.HIVconsV administered IM to groups of 10 male and 10 female BALB/c mice on days 1, 15 and 29. Vaccinations were not associated with any systemic toxicological changes.

Pre-clinical immunogenicity. In pre-clinical studies in BALB/c mice, the second generation core immunogens **M3+M4** together showed equivalent immunogenicity to the first generation MVA.HIVconsV. A single **M3** immunization induced an average response of almost 4000 SFU/ 10^6 splenocytes. HIV-specific T-cell responses were detected against 6 of 10 peptide pools containing overlapping peptides spanning the tHIVconsVX immunogen, indicating breadth of T cell responses. When tested in a combination prime-boost regimen with recombinant simian adenoviruses also expressing tHIVconsVX immunogens, no T-cell responses were detected against junctional sequences in BALB/c and C57BL mouse strains (47).

2.2.4 Clinical Experience with MVA-Vectored Vaccines in HIV Positive Populations

Recombinant MVAs expressing both HIV and non-HIV immunogens (TB) have been tested in 12 studies in the proposed study population of HIV-infected durably ART suppressed participants, in part summarized in [Error! Reference source not found.](#).

MVA.HIVA. The HIVA immunogen was also designed at the University of Oxford, and comprises a consensus clade A gag p24/p17 and a string of clade A-derived CTL epitopes (61). MVA.HIVA has been given to both HIV seronegative and positive individuals. In HIV-uninfected volunteers, MVA.HIVA was shown to be safe in > 400 healthy HIV-uninfected volunteers across different trials (62). Vaccinations were administered ID, IM and subcutaneous (SC) routes at doses ranging from 5×10^7 - 2.5×10^8 pfu (63). No SAEs attributed to the vaccine were observed (reviewed in (62)).

The safety and tolerability of MVAs expressing HIV and non-HIV antigens has also been demonstrated in HIV-1-infected individuals ([Error! Reference source not found.](#)). Among 16 HIV-1-infected persons receiving ART for at least 12 months with a CD4 count > 300 cells/ μ l and plasma viral load < 50 copies/ml who received two ID injections of

MVA.HIVA (5×10^7 pfu) four weeks apart, there were no SAEs in 192 person months of follow-up (58, 64). MVA.HIVA was also safely administered to 20-week-old infants born to HIV-uninfected and HIV-infected mothers in Kenya (24).

MVA.tHIVcons. In the HIV-CORE 001 study of MVA.HIVcons only ([Error! Reference source not found.](#)) in which HIV-1-infected participants on ART were randomized to receive 3 doses of MVA.HIVcons (5 $\times 10^7$ pfu or 2 $\times 10^8$ pfu) or placebo, there were no treatment-related SAEs or SUSARs. In this study, injection site reactions/AEs were the most commonly observed local AE and all were graded as mild or moderate. Systemic AEs observed were all mild or moderate, with malaise the most commonly reported in 7 of 15 vaccinated participants (IB, MVA.tHIVcons3 version 2.0; IB, MVA.tHIVcons4 version 2.0).

MVA expressing HIVcons has been given to 213 participants (269 doses) ranging from 5.5 $\times 10^7$ pfu to 2.2 $\times 10^8$ PFU all given IM. The participant groups included HIV-1-seropositive adults, including recently infected individuals with early virus suppression after initiation of ART. There have been no SAEs considered to be possibly or likely related to MVA.tHIVcons. In sum, clinical trial data with MVA.HIVcons administered by IM injection with 2 $\times 10^8$ pfu indicates the vaccine is safe and well-tolerated (MVA.HIVcons Investigator's Brochure Version 7.0, October 10, 2017, [Table 1](#)). The majority of observed AEs (approximately 90%) were mild or moderate in severity and resolved in 24-48 hours following vaccination, with Grade 3 events reported in less than 5% of vaccinees.

Based on these collective data, we consider the risk associated with **M3, M4 or M3+M4** vaccination to be minimal.

2.3 Risk/Benefit Assessment

2.3.1 *Known Potential Risks*

Risks of M3 and M4 vaccines

Based on safety data from studies with earlier generations of the MVA.HIVcons vaccines and other MVA-vectored vaccines, adverse reactions (AEs) to **M3** and **M4** vaccine are anticipated to involve transient Grade 1 and 2 local reactions such as pain or erythema at the injection site in addition to headache, malaise, and fever (IB, MVA.tHIVcons3 version 2.0; IB, MVA.tHIVcons4 version 2.0). There have been no SAEs or SUSARs in several studies of MVA.HIVcons administered in combination with other vaccines (IB, MVA.tHIVcons3 version 2.0; IB, MVA.tHIVcons4 version 2.0).

Clinical trial data with MVA.HIVcons administered by IM injection with 2 $\times 10^8$ pfu indicates that the following AEs may occur in some participants: injection site tenderness, erythema, swelling, pruritus, induration, myalgia, headaches, dizziness, fatigue, fever,

malaise, nausea, chills, vomiting, flu-like symptoms, diarrhea, sweating, anorexia, abdominal pain, and/or syncope.

Standard local (**Error! Reference source not found.**) and systemic reactions (**Table 5**) can occur, with most appearing within the first 24 hours and usually subsiding within 48 – 72 hours.

Table 4 Local Reactions

Injection site erythema (redness)	Injection site pruritus (itching)
Injection site tenderness	Injection site swelling
Warmth at injection site	Skin discoloration
Injection site pain	Skin damage (vesiculation or ulceration)
Induration (hardening or formation of a crust or scab)	

Table 5 Systemic Reactions

Vomiting	Fatigue (extreme tiredness)
Malaise	Headache
Flu like symptoms	Temperature (fever >37.7°C or 99.9°F)
Sweating	Chills
Diarrhea	Abdominal pain
Dizziness	Myalgia (muscle pain)
Anorexia	Nausea
Syncope	

The expectation is that these AEs will be primarily mild in severity; however, occasional moderate or severe AEs (local pain, headache, malaise, diarrhea, myalgia) have occurred in other vaccine studies with MVA.HIVcons.

Due to lack of experience in humans, there is no information available about the relationship of AEs to the administration of **M3** or **M4** vaccines.

A potential concern regarding the safety of live attenuated viral vaccines is the possibility of pathogenesis, caused by viral mutation and replication. Any potential risk in this respect arising from the administration of **M3** or **M4** is thought to be very small, due to the avirulence and restricted replication of the parental virus MVA and the recombinant vaccine viruses MVA.tHIVcons3 and MVA.tHIVcons4 in human cells.

Animal reproduction studies have not been performed and human data on use during pregnancy are not available. Therefore, the vaccine should not be administered to pregnant women or women with the intention to become pregnant.

As with any other vaccine, Guillain-Barré Syndrome (GBS) or immune-mediated reactions may occur that can lead to organ damage. These problems, however, are very rare events and have never occurred with recombinant MVA-vectored vaccines to date.

Risk of Syncope

Syncope (fainting) can occur before or following any vaccination as a stress response to the needle injection.

Risks of Blood Drawing

Blood drawing may cause pain and bruising and may infrequently cause a feeling of lightheadedness or fainting. Rarely, it may cause infection at the site where the blood was drawn. Problems from use of an intravenous (IV) for blood drawing are generally mild and may include pain, bruising, minor swelling or bleeding at the IV site, and rarely, infection, vein, or blood clot (phlebitis). We minimize risk by using sterile technique and universal precautions.

Overdose

Overdose of **M3** and **M4** is not addressed given all doses will be provided and administered by licensed study staff only and as prepared by the manufacturing facilities.

Risks Associated with Leukapheresis

These include common side effects similar to blood drawing. However, more serious side effects could occur such as flushing, infection due to contaminated equipment, and damage to red blood cells. These serious side effects occur in less than 1 in 10,000 procedures. No such serious adverse events have occurred in our prior studies, in now more the 400 cell collections from HIV+ donors at UNC.

The following are the most common:

- Pain or bruising at the site of needle sticks,
- Phlebitis - Formation of a blood clot at the blood draw site,
- Citrate toxicity (10%),
- Oral paresthesia (tingling around the mouth),
- Paresthesia (tingling/cramping in hands, fingertips, and feet),
- Stiffness in the arms due to the immobilization during donation,
- Fatigue or tiredness, and

- Temporary fluctuations in blood pressure or heart rate.

Less common:

- Infiltration – the needle dislodges and comes out of the vein causing the fluid to go into the tissue,
- Muscle aches or cramps,
- Chills,
- Fever,
- Nausea or vomiting,
- Lightheadedness or headache, and
- Vasovagal reaction resulting in decrease in blood pressure and heart rate.

Rare:

- Seizures or fainting,
- Transient weight gain, ankle swelling, or increased urination for 24 hours due to fluid retention,
- Infection due to contamination of equipment,
- Skin rashes, flushing, or other allergic responses,
- Damage to or loss of red blood cells due to machine malfunction, and
- Remote possibility of air entering the vein and causing chest pains, shortness of breath or shock or death.

Risks Associated with Lymph Node Biopsy Procedure

- Serious complications after fine needle aspirations (FNA) or lymph node biopsies are rare.
- Minor bleeding under the skin at the biopsy site can occur. This can result in a tender, swollen area called a hematoma.
- Infection at the biopsy site is rare because of the use of sterile techniques and equipment.
- Common Local Reactions
 - Swelling,
 - Soreness, and
 - Pain - typically treated with acetaminophen (Tylenol).

Unknown Risks

New therapies can lead to unexpected, incidental finding that could have a potential effect on the participant's health. Upon confirmation of a potential health or reproductive effect, the study team will notify participants impacted by the new information and will advise

proper medical follow-up when indicated. If findings require more immediate medical attention, the study PI in conjunction with the study coordinators will assist participants in getting an appropriate care appointment.

2.3.2 *Known Potential Benefits*

The addition of the **M3**, **M4**, or combined **M3+M4** to a person's ART regimen and the donation of one's blood cells to this research study provides no direct medical benefits to participants. However, participation contributes to ongoing HIV research, potentially resulting in new treatments for HIV infection.

2.3.3 *Assessment of Potential Risks and Benefits*

Given that many HIV-1-infected patients on effective ART have persistent low-level viremia that can be detected by ultrasensitive research assays and exhibit impaired HIV-1 specific immune responses, interventions with the potential to improve HIV-specific T-cell responses and limit viremia should be tested. Therapies that improve clearance of persistently HIV-1-infected cells will likely be a necessary component of any HIV remission or eradication strategy. Based on the data outlined above, there is sufficient expectation that the proposed treatment interventions will be safe and well tolerated. Although participants in this early phase study will receive no direct benefit for their participation in this study, there remains a strong desire among HIV-infected individuals, and the HIV community at-large, to pursue HIV preventative and therapeutic vaccine strategies. The potential adverse effects, stigmatization, and financial costs encountered by HIV-infected persons receiving life-long antiretroviral therapy along with the potential harm of persistent immune activation/inflammation are strong reasons to pursue HIV vaccine research. In short, an HIV cure or sustained remission in the absence of ART remain desirable goals that would have substantial benefits for many individuals if achieved. An effective HIV vaccine represents a key strategy for both HIV prevention and cure.

3 OBJECTIVES AND ENDPOINTS

OBJECTIVES	ENDPOINTS	JUSTIFICATION FOR ENDPOINTS
Primary		
Evaluate the safety of vaccination with M3 or M4 or M3+M4 in HIV-1 infected participants on ART with plasma HIV-1 RNA <50 copies/mL.	Safety Occurrence of at least one \geq Grade 3 Adverse Event (AE) including signs/symptoms, lab toxicities, and/or clinical events, that is possibly or	The study will use standard safety grades used in HIV clinical trials. If exceeded, it is currently felt that such risks would be

OBJECTIVES	ENDPOINTS	JUSTIFICATION FOR ENDPOINTS
	
definitely related to study treatment any time from the first day of treatment through 28 days following vaccination. Safety data will include local and systemic signs and symptoms, laboratory measures of safety/toxicity, and all adverse and serious adverse events. Safety data will be routinely collected throughout the duration of the study.
 
NOTE: The occurrence of a Grade 3 elevated blood pressure during a study-related leukapheresis that resolves following completion of the procedure will not be included as a primary safety endpoint.
	unacceptable in a research study of this nature.

OBJECTIVES	ENDPOINTS	JUSTIFICATION FOR ENDPOINTS
Secondary		
Evaluate the safety of vaccination with M3 or M4 or M3+M4 in HIV-1 infected participants on ART with plasma HIV-1 RNA <50 copies/mL.	Occurrence of any \geq Grade 1 AE including signs/symptoms, lab toxicities, and/or clinical events, that is possibly, probably, or definitely related to study treatment any time from the first day of treatment through Day 168 (Week 24) following vaccination.	
Compare the within-participant relative change in magnitude of HIV-1-specific T cell responses in participants following vaccination with either M3 or M4 or M3+M4 .	Relative changes in magnitude of T cell responses to HIV-1 conserved regions measured by ex vivo IFN- γ ELISpot from pre-vaccination on Day 0 to post-vaccination on Day 7 and 14.	Previous studies indicate that the rMVA-induced T cell response, typically measured by ex vivo IFN-γ ELISpot, peaks between day 7-14 days following vaccination.
Compare the between-arm change in breadth of HIV-1-specific T cell responses in participants from pre-vaccination to post-vaccination with M3 or M4 or M3+M4 .	Change in breadth of T cell responses targeting HIV conserved regions from pre-vaccination (Day 0) to post-vaccination at Day 28.	We hypothesize that the greater sequence coverage conferred by M3+M4 vaccination will breadth of HIV-specific T cells that will remain detectable over time.
Tertiary/Exploratory		
1. Compare the change in function and phenotype of HIV-1-specific T cell responses in participants from pre- to post-vaccination with either M3 or M4 or M3+M4.	1. Relative change in magnitude and phenotype of HIV-1-specific CD8 $^{+}$ T cell populations, including tetramer reactivity, from pre-vaccination (Day 0) to	Tertiary endpoints 1-3 will explore how MVA vaccination impacts T cell function and phenotype and whether this manifests as increased in vitro

	post-vaccination at Day 7 and 14 by flow cytometry.	clearance of HIV-infected CD4⁺ T cells.
2. Evaluate the kinetics of immunologic responses in participants' pre- and post-vaccination with either M3 or M4 or M3+M4 .	2. Describe the magnitude and phenotype of HIV-1-specific CD8 ⁺ T cell populations at multiple pre- and post-vaccination time points by flow cytometry.	
3. Evaluate the kinetics of CD8 ⁺ T cell mediated HIV inhibition in participants pre- and post-vaccination with either M3 or M4 or M3+M4 .	3. Relative change in HIV p24 levels in CD4 ⁺ T cells at multiple pre- and post-vaccination time points by virus inhibition assay.	
4. Explore cellular activation status of total CD4 ⁺ and CD8 ⁺ T cells pre- and post-vaccination with either M3 or M4 or M3+M4 .	4. Describe the cellular activation status of CD4 ⁺ and CD8 ⁺ T cell subsets at multiple pre- and post-vaccination time points by flow cytometry.	Exploratory endpoint 4 examines whether MVA vaccination induces general activation of T cell subsets. This will inform the timing of treatments in future combination studies with other immunotherapies or LRAs.
5. Explore the impact of vaccination with either M3 or M4 or M3+M4 on low-level plasma viremia.	5. The proportion of participants in whom HIV-1 plasma RNA decreases from pre-vaccination (geometric mean of Day -60 and 0) to post-vaccination (geometric mean of Day 56 and 70) as measured by single copy assay.	Exploratory endpoints 5–7 examines whether MVA vaccination has an in vivo effect on persistent HIV infection.

OBJECTIVES	ENDPOINTS	JUSTIFICATION FOR ENDPOINTS
Tertiary/Exploratory		
6. Explore the impact of vaccination with either M3 or M4 or M3+M4 on cell-associated HIV RNA in CD4+ T cells. 7. Explore the impact of vaccination with either M3 or M4 or M3+M4 on total viral DNA in CD4+ T cell.	6. The proportion of participants in whom cell-associated RNA in total CD4+ T cells decreases post-vaccination (geometric mean of Day 28 and Day 56) compared to pre-vaccination (geometric mean of Day -45 and Day 30.) 7. Proportion of participants in whom total HIV DNA in total CD4+ T cells decreases post-vaccination (geometric mean of Day 28 and Day 56) compared to pre-vaccination (geometric mean of Day -45 and Day 30.)	Exploratory endpoints 5–7 examine whether MVA vaccination has an in vivo effect on persistent HIV infection.

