9.3.4 Analysis of the Secondary Endpoint(s)

9.3.5 Immunological and Virologic Analysis

To evaluate changes in HIV-1 epitope-specific CD8⁺ T cell responses detected in IFN- γ ELISpot assays before and after vaccination, the relative change within participants (from Day 0 to both Day 7 and Day 14) will be estimated using a geometric mean ratio and evaluated with an exact 2-sided Wilcoxon signed-rank test. If the symmetry assumption for change in natural log-transformed summed HIV-1 specific T cell response appears violated, a sign test will be conducted as a sensitivity analysis. Efficacy and exploratory endpoints defined as a proportion of participants will be analyzed with a 2-sided binomial 95% CI. Within a vaccination arm, changes in continuous measurements over time (e.g., change in an immune parameter from baseline to post-vaccination) will be summarized graphically and evaluated with an exact 2-sided Wilcoxon signed-rank test, or a sign test for endpoints that appear to violate assumptions of the Wilcoxon test.

Observed immunologic measurements, such as the change in breadth following vaccination, may not be normally distributed or may be partially censored due to assay limits of quantification, and thus, an exact Wilcoxon rank-sum test will be used for between-arm comparison.

The focus of our **secondary** objectives is to examine the effect of vaccination on within-participant T cell magnitude and between-arm breadth of HIV-specific T cell responses.

9.3.6 T cell Magnitude:

The primary *within arm* outcome will be the summed HIV-specific T cell response, either to peptides pools spanning the immunogen or pools of optimal HIV CD8⁺ epitopes. HIV specific T cell responses will be measured at baseline, Day 7, and Day 14 (following **M3, M4, or M3+M4** vaccination). An average fold change of at least 2 (comparing T cell responses within participant) was anticipated to be scientifically meaningful. The specific alternative hypothesis is a geometric mean ratio (GMR) of 2. The assumed between-participant standard deviation (SD) for natural log-transformed HIV-specific T cell response was estimated from previous baseline data derived from HIV-infected participants durably suppressed by ART sampled weekly or monthly. Data were provided by [name] (66). Empirical power for the exact Wilcoxon signed-rank test was calculated using 100,000 simulated datasets assuming natural log-transformed HIV-specific T cell

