Virologic measures: Virologic measures such as cell-associated HIV-1 RNA will be log-transformed prior to analyses. Appropriate analysis method will be used for plasma HIV-1 RNA by SCA depending on the amount of results below assay limit. For example, if a substantial fraction (~50%) are below the assay limit, the analysis will focus on estimating the proportion of participants with detectable SCA at various time points and comparison between arms will use Fisher's exact test; otherwise, changes within participants will be summarized and compared between arms using Wilcoxon rank-sum tests.

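### Exploratory endpoints 5-7 count any decrease and have no reference proportion, and the log-scale change analyses planned elsewhere are not tied to them

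*Combined protocol and SAP*

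**What the plan says.** Section 3, Tertiary/Exploratory, defines three virologic endpoints as proportions:

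- Endpoint 5: "The proportion of participants in whom HIV-1 plasma RNA decreases from pre-vaccination" (geometric mean of Days -60 and 0) to post-vaccination (Days 56 and 70), by single copy assay (SCA).
- Endpoint 6: "The proportion of participants in whom cell-associated RNA in total CD4+ T cells decreases post-vaccination".
- Endpoint 7: "Proportion of participants in whom total HIV DNA in total CD4+ T cells decreases post-vaccination".

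Endpoints 6 and 7 use Days 28 and 56 as the post-vaccination mean. Their pre-vaccination mean is printed as Day -45 and Day 30. The stated purpose of endpoints 5-7 is to "examine whether MVA vaccination has an in vivo effect on persistent HIV infection".

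Section 9.3.5 says: "Efficacy and exploratory endpoints defined as a proportion of participants will be analyzed with a 2-sided binomial 95% CI". The next sentence says that within-arm changes in continuous measurements "will be summarized graphically and evaluated with an exact 2-sided Wilcoxon signed-rank test", or with a sign test where the assumptions look doubtful. Section 9.3.10 adds: "Virologic measures such as cell-associated HIV-1 RNA will be log-transformed prior to analyses". For SCA it plans Fisher's exact test on detectability if about half the results are below the limit; "otherwise, changes within participants will be summarized and compared between arms using Wilcoxon rank-sum tests". Section 9.3.2 sets a 0.05 level without multiplicity adjustment and puts the emphasis on effect sizes and description. Allocation is 7:7:7:3.

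**The concern.** A fall of any size counts the same as a large one, and nothing says what proportion would be expected without a vaccine effect. The endpoints are meant to show whether vaccination affects persistent infection, and a bare proportion cannot do that unless the no-effect proportion is known. In arms of 7, a majority with some decrease is an ordinary chance result, and three vaccine arms by three endpoints give nine such proportions.

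The choice also departs from the rest of the plan. Exploratory endpoints 1 and 3 are defined as relative changes. The pre and post geometric means needed for a ratio are already part of endpoints 5-7. What is at stake is how an exploratory virologic result is read when the next combination study is planned. No decision rule in the plan depends on these endpoints.

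**Working it through.** **Plan's own figures.** No precision or power is stated for endpoints 5-7. The nearest figures are the one-sided 95% exact binomial upper limits at n=7 in section 9.2.1. For 0/7, 1 - 0.05^(1/7) = 34.8% (stated 35%). For 1/7, the 0.95 quantile of Beta(2, 6) is 52.1% (stated 52%). Both reproduce.

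**Chance of a majority decreasing.** Inputs: n=7 per vaccine arm (section 4.1, Table 6). Assumption: no effect, no ties, no drift, so P(decrease) = 0.50.

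- P(X ≥ 5) = (21 + 7 + 1)/128 = 22.7%
- P(X ≥ 6) = 8/128 = 6.25%
- P(X = 7) = 1/128 = 0.8%
- At least one of three vaccine arms with 5/7 or more: 1 - (1 - 0.227)^3 = 53.7%
- At least one of nine arm-by-endpoint proportions, treated as independent: 90% for 5/7 or more, 44% for 6/7 or more, 6.8% for 7/7. The three endpoints come from the same participants, so independence is only a rough guide.

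**How far 0.50 can be trusted.** It is not a figure from the documents. With tie rate t (for example, both means below the assay limit), P(decrease) = (1 - t)/2. With a natural decline of d standard deviations (SD) of the change, P(decrease) = Φ(d). The values of t and d are assumptions.

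| Assumption | P(decrease) | P(≥5/7) |
|---|---|---|
| no ties, no drift | 50% | 22.7% |
| 20% ties | 40% | 9.6% |
| 30% ties | 35% | 5.6% |
| 50% ties | 25% | 1.3% |
| decline of 0.1 SD | 54% | 29.7% |
| decline of 0.25 SD | 60% | 41.7% |
| decline of 0.5 SD | 69% | 62.8% |

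**What the planned interval shows.** Two-sided exact 95% limits at n=7: 5/7 gives 29.0-96.3%, 6/7 gives 42.1-99.6%, 7/7 gives 59.0-100%. Only 7/7 excludes 50%. For 21 pooled vaccinees, 14/21 gives 43.0-85.4% (two-sided p = 0.19 against 50%), and 16/21 is the smallest count whose interval excludes 50% from below (52.8-91.8%).

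**Placebo as reference.** With n=3, 1/3 decreasing has an interval of 0.8-90.6%. Fisher's exact p for 7/7 is 0.008 against 0/3, 0.067 against 1/3 and 0.30 against 2/3.

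**What dichotomising costs.** Assumptions: normal changes, a true fall of 0.6 SD, no ties, two-sided 0.05. Then P(decrease) = Φ(0.6) = 0.726.

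- n=7, sign test: rejects only at 0/7 or 7/7, so power = 0.726^7 + 0.274^7 = 10.6%. Exact signed-rank test (simulated): 25%.
- n=21, sign test: rejects at ≥16 or ≤5, power 46%. Exact signed-rank test (simulated): 71%.

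**The case against.** The strongest reply is that most of the remedy is already in the plan. The sentence after the binomial-interval sentence in section 9.3.5 provides signed-rank or sign tests for continuous changes, under a heading that covers virology. Section 9.3.10 log-transforms virologic measures and, for SCA, compares changes between arms. A sign test is a comparison with 50%, and there is a randomized placebo arm. The planned intervals at 5/7 and 6/7 both include 50%, and section 9.3.2 warns about small samples and unadjusted results. The power contrast is clearest at n=21, yet the plan describes pooling of vaccine arms for safety, not for virology.

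Much of this stands. A reader might infer that the plan discards the size of the change altogether, or has no reference of any kind; sections 9.3.5 and 9.3.10 and the placebo arm show otherwise. A reader might also take 50% as the chance level for all three endpoints. The documents do not support that, least of all for endpoint 5, where section 9.3.10 itself allows for about half the SCA results being below the limit.

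What remains is the gap between definition and analysis. The declared endpoint is the proportion, its stated analysis is an interval with no comparator, and no between-arm comparison is spelled out for endpoints 6 and 7 or for the proportion decreasing. Three placebo participants are too few to supply the missing reference.

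**Conclusion.** The point holds as a limited one. The declared form of endpoints 5-7 ignores how large the change is and states no reference proportion, and the better analyses elsewhere in the plan are not attached to them. A result of 5/7 or better has a 23% chance per arm without ties or drift. Under the assumptions tabulated, that falls to 1.3% with 50% ties and rises to 63% with a 0.5 SD natural decline. This spread is the main reason why the proportion cannot be interpreted alone.

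The gain from a continuous summary (46% to 71% power at n=21) rests on an assumed 0.6 SD fall, normal changes, no ties and pooling. Per arm, 10.6% against 25% is inadequate either way. The importance is low, because the endpoints are exploratory and no decision depends on them.

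The Day 30 in the pre-vaccination baseline of endpoints 6 and 7 conflicts with vaccination at Day 0. It falls after the Day 28 sample that the same endpoints count as post-vaccination. It may be a lost minus sign; the documents do not settle it.

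**What to change.** 1. For endpoints 6 and 7, and for endpoint 5 when most SCA values are quantifiable, make the within-participant log ratio of post to pre geometric means the main summary. Report the geometric mean ratio with a 95% interval and exact signed-rank test, by arm and pooled over the 21 vaccinees, with the placebo values shown alongside.
2. Keep the proportion decreasing as descriptive only. Count pairs below the limit at both times as ties, and exclude them before any comparison with 50%.
3. Keep the detectability fallback for SCA in section 9.3.10.
4. Reconcile the printed baseline days for endpoints 6 and 7 with vaccination at Day 0 before any ratio is computed.

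The cost is analysis-plan wording; no new samples or visits are needed. There are two small downsides: a rule for censored values must be written, and pooling assumes similar effects across the three vaccine arms, so the by-arm results should stay beside it.
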